
i) Data Analysis

Aim 1 - To assess the effects of virus type on progression to acute bacterial sinusitis, the type and number of background asymptomatic viruses, the season, and the interaction of season and background asymptomatic viruses and demographic variables, we will fit a generalized linear model to the URI episode data (1500 observations on 300 children, 0 = non progressing, 1 = progressing) using child as the main sampling unit and assuming a binomial distribution for the data. It is anticipated that the average number of URI episodes per child will be 5 per year. This model accounts for the potential correlation among the multiple episodes in each child. For predictors which take values of yes or no (such as virus type), we will have 80% power to detect the

difference between the percent of a particular virus type equal to 30% for the acute bacterial sinusitis group and 45% for the control group. We will test that rhinovirus is the most common viral URI to predispose to acute bacterial sinusitis using a Chi-squared test for goodness of fit. If rhinovirus accounts for 40% of the URIs leading to sinusitis and the second most common leads to 20% or less then we will have 80% power to conclude that rhinovirus is the most common viral antecedent to acute bacterial sinusitis.

The specimens obtained at baseline and during four other surveillance periods (approximately 1500 - 1800 specimens) will allow us to determine the changes due to season in background level of asymptomatic viral infection and the diversity of viruses. We will use robust multinomial regression using the R package multinomRob that accounts for over-dispersion due to the clustering of the URI episodes within children. This method of modeling multinomial data will allow us to assess the effect of season and the demographic variables on asymptomatic background viruses.

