To estimate the incidence of acute bacterial sinusitis as a complication of URI we will use a random effects generalized linear model assuming binomial distribution. We expect a total of 1500-1800 episodes of URI among the children and hypothesize that ABS will complicate 8% of these cases resulting in approximately 120 cases of acute bacterial sinusitis. If the true percent of viral URIs progressing to acute bacterial sinusitis is 8% then 1500 cases will give us 80% power to estimate the incidence with a 95% confidence interval no longer than 2.9%. If we were to observe exactly the 8% incidence the 95% confidence interval would be (6.68%, 9.49%).

Aim 2 - The episodes of acute bacterial sinusitis and uncomplicated URI chosen for PhyloChip analysis will be from two groups. The “acute bacterial sinusitis group” will consist of the first episode of acute bacterial sinusitis occurring among 50 randomly selected children who have one or more episodes of acute bacterial sinusitis. Only the first episode will be eligible to avoid data clustered within child. To avoid running all the PhyloChip analysis at the end of the study we will select the children in groups of 10 evenly spaced over the 52-months of enrollment and follow-up. An additional 50 matched control cases of uncomplicated URI will be selected (10 at a time) from the group of children who have not yet had an episode of acute bacterial sinusitis. The controls will be chosen so that their uncomplicated URI closely matches the case of acute bacterial sinusitis in calendar time. If a control child later develops acute bacterial sinusitis, the control child will become eligible to be chosen for the acute bacterial sinusitis group. If this occurs a different matched control will be chosen as a replacement. This process will result in a few extra PhyloChips being run but is necessary as the processing of PhyloChips is time consuming and cannot be delayed until the end of the study. In addition, the surveillance sample most closely preceding the episode of acute bacterial sinusitis and uncomplicated URI will also be analyzed using the PhyloChip.

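### The Aim 1 incidence interval (6.68%, 9.49%) and the 2.9-point precision statement treat 1,500 clustered episodes as independent; the 80% power for virus type also lacks a stated basis

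*Protocol*

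**What the plan says.** All of this is in the protocol, section i) Data Analysis, Aim 1.

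- **Data structure.** The episode data are described as "1500 observations on 300 children, 0 = non progressing, 1 = progressing", and it is anticipated that "the average number of URI episodes per child will be 5 per year". Of the model for risk factors the protocol says: "This model accounts for the potential correlation among the multiple episodes in each child".
- **Incidence.** For this estimate "we will use a random effects generalized linear model assuming binomial distribution". The expected yield is that "ABS will complicate 8% of these cases resulting in approximately 120 cases of acute bacterial sinusitis".
- **Precision.** With 1,500 episodes and a true value of 8%, the protocol claims 80% power for a 95% interval no longer than 2.9 points. It adds: "If we were to observe exactly the 8% incidence the 95% confidence interval would be (6.68%, 9.49" (the upper limit is 9.49%).
- **Virus type.** Power of 80% is claimed for binary predictors, of which virus type is one; the target is a "difference between the percent of a particular virus type equal to 30% for the acute bacterial sinusitis group and 45% for the control group".

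No intraclass correlation or design effect accompanies any of these figures. The virus-type sentence also gives no group sizes and no significance level.

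**The concern.** The incidence of sinusitis as a complication of URI is primary objective 1a. Its planned precision should reflect the analysis that will be done, which is a random effects model because each child contributes several episodes. If a child's episodes are positively correlated, 1,500 episodes carry less information on the overall proportion than 1,500 independent ones, and the interval widens. A precision statement computed as if they were independent then promises more than the study can be expected to deliver.

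The virus-type power supports primary objective 1b. The obvious inputs in the same section do not return its 80%, so a reader cannot tell what was assumed.

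**Working it through.** **Inputs from the protocol:** 1,500 episodes, 300 children, 5 episodes per child, 8% progression (120 cases, hence 1,500 − 120 = 1,380 non-progressing episodes), 30% against 45% for virus type. **Assumed:** two-sided alpha 0.05 for the virus-type comparison, and the intraclass correlations (ICC) below.

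**Step 1. Reproduce the stated interval.** Exact (Clopper-Pearson) limits for x = 120, n = 1,500:
- lower = 2.5% quantile of Beta(x, n − x + 1) = Beta(120, 1381) = 6.68%
- upper = 97.5% quantile of Beta(x + 1, n − x) = Beta(121, 1380) = 9.49%

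The length is 2.81 points. This is an exact match, with no allowance for clustering.

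**Step 2. Reproduce the 2.9-point statement.** With n = 1,500 the exact interval is at most 2.9 points long when there are 128 cases or fewer (length 2.895 at 128, 2.905 at 129). For X ~ Binomial(1500, 0.08), P(X ≤ 128) = 79.2%, which matches the stated 80%. This figure too assumes independent episodes.

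**Step 3. Allow for clustering.** Use DE = 1 + (m − 1) × ICC with m = 5, replace 1,500 by 1,500/DE, and repeat steps 1 and 2 (effective number rounded to a whole number for the probability).

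| DE | ICC | Effective episodes | 95% interval at 8% | Length (points) | Chance of length ≤ 2.9 |
|---|---|---|---|---|---|
| 1.00 | 0 | 1,500 | 6.68% to 9.49% | 2.81 | 79% |
| 1.05 | 0.0125 | 1,429 | 6.65% to 9.53% | 2.88 | 55% |
| 1.10 | 0.025 | 1,364 | 6.62% to 9.57% | 2.95 | 33% |
| 1.20 | 0.05 | 1,250 | 6.56% to 9.64% | 3.09 | 8% |

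**Step 4. Virus-type power.** Two-proportion z-test with pooled null variance, 120 against 1,380 episodes:
- pooled proportion = (120 × 0.30 + 1,380 × 0.45)/1,500 = 0.438
- SE under the null = √[0.438 × 0.562 × (1/120 + 1/1,380)] = 0.0472
- SE under the alternative = √[0.30 × 0.70/120 + 0.45 × 0.55/1,380] = 0.0439
- power = Φ[(0.15 − 1.96 × 0.0472)/0.0439] = Φ(1.31) = 90.5%

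Other standard versions at two-sided 0.05 (continuity-corrected, unpooled, arcsine, Fisher, logistic) run from 88.6% to 92.7%. With the same group sizes, 80% power is reached at about 32% against 45% (79.9%).

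**The case against.** **The virus-type benchmark is not the planned analysis.** The protocol plans an adjusted model with the child as sampling unit, and such a model can have less power than an unadjusted test on independent episodes. The 1,380 and the alpha of 0.05 are inputs supplied here, not stated there. This stands: 80% is not shown to be an error, and since it lies below the naive 90% it is conservative.

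**A stronger reading is tempting.** A reader might infer that the 80% conceals a design effect of about 1.34, which does bring 90.5% down to 80%. The protocol would then have allowed for clustering in one figure and omitted it from the next. The document does not support this. The value is only back-solved, and other unstated choices land in the same place: two controls per case (120 against 240) gives 79.1%; a virus found in 75% of episodes (90 against 1,035) gives 80.2%; a covariate R-squared of about 0.24 in a logistic model also gives 80%. Even if 1.34 had been used for virus type, it would not carry over to the incidence. Virus type varies between episodes of the same child, so its design effect need not equal that of an overall proportion.

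**More episodes may accrue.** The protocol expects 1,500 to 1,800. At 1,800 a design effect of 1.2 leaves 1,800/1.2 = 1,500 effective episodes, which returns the stated interval. This is true, but the protocol ties its 2.9-point statement to 1,500.

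**Design inputs often sit in the SAP.** That may explain missing detail. It does not explain figures printed in the protocol that do not match the model named in the same paragraph.

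**Conclusion.** The point holds for the incidence precision. The interval and the 2.9-point statement are reproduced exactly by assuming independent episodes, while the section that prints them expects repeated, possibly correlated episodes per child and plans a random effects model. The widening is small in absolute terms, 0.07 to 0.28 points for design effects of 1.05 to 1.20. But the naive length is only 0.09 points below the limit, so the claimed 80% falls to 55%, 33% and 8% at design effects of 1.05, 1.10 and 1.20. These values are illustrative: they assume positive correlation, equal numbers of episodes per child and the effective-sample-size approximation. The protocol gives no ICC from which to choose among them.

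The virus-type power is a secondary matter of an undocumented basis. It is not an overstatement of power, and nothing about clustering can be inferred from it. Neither point affects the sample size, the analysis model or the conduct of the study.

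**What to change.** 1. Recompute the incidence interval and the 2.9-point statement under the planned random effects model, with a stated ICC or design effect, or over a range such as the one tabulated above. Accept the slightly wider figure; for example, a design effect of 1.10 gives 6.62% to 9.57%, a length of 2.95 points.
2. For the 30% against 45% comparison, state the group sizes, alpha and any ICC or covariate adjustment behind the 80%. Otherwise restate it as about 90% for 120 against 1,380 independent episodes at two-sided 0.05, or as 80% for about 32% against 45%.
3. Choose the two clustering assumptions separately; they need not be equal.

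The cost is a few recalculated sentences. No change to enrolment, data collection or the analysis model is needed.

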- We will enroll and follow eligible children between ≥ 4 through < 8 years of age prospectively for one year. Using high-throughput multiplex PCR-based viral diagnostics, the identities of antecedent viral infections will be determined for each symptomatic URI, and during four surveillance periods. We hypothesize that rhinovirus will be the most common viral URI to predispose to acute bacterial sinusitis. This information can potentially direct the development of antiviral medication or viral vaccines.
- Using stringent clinical definitions for acute bacterial sinusitis, we will determine the incidence of sinusitis as a complication of viral URI. This has not been previously determined

and we hypothesize that sinusitis will complicate viral URI in 8% of cases in these young children.

Aim 2: To define relationships between the nasopharyngeal microbiome, viral illnesses, and progression to clinical sinusitis.

Nasopharyngeal samples and a pilot number of stool samples obtained before, during and after viral respiratory infections will be analyzed for bacterial species using array-based diagnostics (PhyloChip) and conventional semi-quantitative microbiologic techniques in two groups of children:

- a) those with viral URIs that resolve spontaneously and
- b) those whose URI progresses to acute bacterial sinusitis.

We hypothesize that the presence and density of sinopathogens and inhibitory commensal microbiota, together with modifications caused by infection with common respiratory viruses, will influence the likelihood of progression to acute bacterial sinusitis. Knowledge of these predictive elements will direct preventive strategies and treatment decisions.

The primary objectives of the study are as follows:

1. To determine a) the incidence of acute bacterial sinusitis in children ≥ 4 through < 8 years of age as a complication of an antecedent viral URI, b) if certain viruses are more likely than others to precipitate an episode of bacterial sinusitis and c) what percentage of sinus infections are, in fact, preceded by viral infection.

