S. pneumoniae will be identified by using the optochin disk susceptibility test (Taxo P, Becton Dickinson Microbiology Systems); *S. pneumoniae* isolates will not be serotyped. *M. catarrhalis* will be identified by the API QuadFerm assay (bioMerieux, Inc., Hazelwood, MO, USA), and NT- *H. influenzae* by the Haemophilus ID Quad Plate with Growth Factors (Becton Dickinson Microbiology Systems).

g) Study Methods-Virus Identification The Respiratory Multicode Assay (RMA) is a high throughput and sensitive multiplex PCR based on unique chemistry (Multicode, EraGen Biosciences), and was developed by researchers at the University of Wisconsin-Madison and EraGen BioSciences (Madison WI).²⁴ This state-of-the-art assay detects the following viruses: human rhinoviruses-A, B, and C, enteroviruses, coronaviruses (including OC43, 229, NL63, and SARS), adenoviruses B, C, and E, influenza A and B, parainfluenza viruses I-IV, respiratory syncytial virus A and B, metapneumovirus, and bocavirus. The assay has been validated against standard viral diagnostics.²⁵ Furthermore, rhinoviruses are expected to cause the majority of URIs in the proposed clinical study and the RMA assay has been proven to detect all 100 rhinovirus serotypes as well as the newly discovered C species. Primers have been refined in accordance with sequence information from over 1000 clinical isolates^{26,27}

h) Preliminary Data:

[figure not shown]
i. Bacterial etiology of acute sinusitis in children and response to antimicrobial agents. In a series of studies done between 1981 and 2009^{2,4,5}, Wald and colleagues have provided meticulous data outlining the three major causes of acute bacterial sinusitis in children (*S. pneumoniae*, *H. influenzae* and *M. catarrhalis*) using the gold standard of sinus aspiration. Using stringent clinical definitions of acute bacterial sinusitis, systematic study comparing antimicrobial to placebo has established the benefit of antimicrobials in enhancing clinical cures, reducing clinical failures and shortening the course of the clinical illness.^{4,28}

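### The goodness-of-fit test for rhinovirus as leading antecedent has no stated cells, null shares or direction, and its 80% power holds only with a single rival virus near 20%

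*Protocol*

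**What the plan says.** The Aim 1 hypothesis is directional: "We hypothesize that rhinovirus will be the most common viral URI to predispose to acute bacterial sinusitis". In the Protocol, section 4, item i) Data Analysis, Aim 1, the planned analysis is to "test that rhinovirus is the most common viral URI to predispose to acute bacterial sinusitis using a Chi-squared test for goodness of fit".

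A power statement comes next. Its condition reads "If rhinovirus accounts for 40% of the URIs leading to sinusitis and the second most common leads to 20% or less"; when that is met, the protocol claims a power of 80% for declaring rhinovirus the leading antecedent. No null shares, number of categories, direction or significance level are given for this test. Nothing is said about how many viruses may lie near 20%.

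Two other places supply inputs. The incidence paragraph of the same section says "We expect a total of 1500-1800 episodes of URI among the children" and, at 8%, puts the yield at "resulting in approximately 120 cases of acute bacterial sinusitis". Item g), Virus Identification, lists the assay targets ("This state-of-the-art assay detects the following viruses: human rhinoviruses-A, B, and C, enteroviruses, coronaviruses", and others). Counted by virus type, these make nine groups: rhinovirus, enterovirus, coronavirus, adenovirus, influenza, parainfluenza, RSV, metapneumovirus and bocavirus.

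**The concern.** A goodness-of-fit test asks whether observed shares depart from a given set of shares. It does not ask which share is largest. If it is run as an omnibus test over the virus groups, it will be significant whenever the shares are clearly unequal, whichever virus leads. The conclusion about rhinovirus would then rest only on which virus happened to have the largest count, with no control of the chance of naming the wrong one.

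The power sentence raises a second question. Its condition limits the share of the second virus but not the number of viruses that may reach that share. If several do, rhinovirus has to beat the largest of several random counts, which is harder than beating one virus named in advance.

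This is the only test named for the rhinovirus hypothesis, and the protocol says under Aim 1 that the information could potentially guide antiviral or vaccine development.

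**Working it through.** **Inputs from the protocol.** Sinusitis episodes: 0.08 × 1500 = 120, or 0.08 × 1800 = 144 at the upper end of the expected range. Rhinovirus share 40%; second virus 20% or less; stated power 80%.

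**Assumptions.** Two-sided 5% (one-sided also tried); exactly one virus per episode; independent episodes; shares of the remaining viruses as listed below. The protocol gives none of these for this test.

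**Step 1: reproduce the 80%.** Take two cells, rhinovirus and one rival, with a 1:1 null. Expected counts at 120 episodes are 48 and 24, total 72, so 36 per cell under the null. Noncentrality = (48 − 36)²/36 + (24 − 36)²/36 = 4 + 4 = 8.0 on 1 df. Power = 80.7% (exact binomial 81.0%). The stated figure reproduces. Against that one rival, power rises as its share falls (about 86% at 19%, about 97% at 15%).

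**Step 2: the ordinary omnibus form.** Null: equal shares over nine groups, 8 df. Noncentrality = 120 × 9 × Σ(pᵢ − 1/9)². With rhinovirus at 40%, one rival at 20% and the rest spread evenly over seven groups, this is about 121 and power is essentially 100%. The omnibus form over nine groups is therefore not the source of the 80%.

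The next table applies the same test where rhinovirus is not the sole leader (120 episodes, 1,000,000 multinomial runs, remainder spread evenly over seven groups). The last column requires rhinovirus (count r) to lead the largest other count o with (r − o)²/(r + o) > 3.84.

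| Rhinovirus vs leading other | Omnibus test rejects | Rejects and rhinovirus has largest count | Rhinovirus beats runner-up |
|---|---|---|---|
| 30% vs 30% (tied) | >99.9% | 48% | 2.5% |
| 25% vs 30% (second) | >99.9% | 21% | 0.3–0.4% |

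**Step 3: power of the runner-up rule inside the stated condition.** Rhinovirus is at 40% in every row; the rule is as in Step 2.

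| Other viruses | 120 episodes, two-sided 5% | 120 episodes, one-sided 5% | 144 episodes, two-sided 5% |
|---|---|---|---|
| One at 20%, rest near 6% | 82% | 89% | 88% |
| 20/15/15/10 | 80% | 88% | 87% |
| Two at 20%, rest small | 72% | 82% | 81% |
| Three at 20% | 65% | 77% | 75% |
| Two at 18%, rest 4% each | 83% | 91% | 90% |
| Three at 18%, one at 6% | 78% | 87% | 87% |

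At two-sided 5%, reaching 80% takes about 142 episodes with two rivals at 20% and about 158 with three.

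**The case against.** The strongest reply is that the power sentence shows what was meant. It names two quantities, rhinovirus and the second virus, and its 80% matches a two-cell test. With direction added, that test does address which virus leads. On this view only the cells, null and direction are missing, and those can go into a statistical analysis plan. This stands in part. A reader might infer that the named test is simply the wrong one and the 80% simply wrong; the documents support neither. The two-cell form is a goodness-of-fit test, and the 80% reproduces from the protocol's own inputs.

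What does not fall away is that the text names a test whose usual form cannot support the stated conclusion. Even on the two-cell reading the rival is not named, so in practice it is whichever virus comes second in the data.

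The limits on the power shortfall also stand:

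- It needs two or more viruses at or very near 20%. With two at 18%, power is 83%.
- Three rivals at 20% use up the whole 100% and leave nothing for the other five groups, so 65% is an extreme case.
- With two rivals at 20%, the shortfall disappears at 144 episodes (81%) or at one-sided 5% (82%).

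Finally, the question whether some viruses are more likely than others to lead to sinusitis is handled by the clustered model in the same section, not by this test.

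**Conclusion.** The point holds in a limited form, with minor to moderate importance.

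The test is under-specified in a way that matters. Read as an omnibus test, a significant result is no evidence that rhinovirus leads: with a true tie at 30% it would be declared the leader in about 48% of runs, against 2.5% under a rule that compares it with the runner-up.

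The 80% is correct for one rival at 20% with the others at about 15% or less. It is not correct across the whole stated condition: at 120 episodes it is about 72% with two viruses at 20% and about 65% with three, and at 144 episodes about 81% and 75%.

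These figures rest on the assumed virus mixes, two-sided 5%, one virus per episode and independent episodes. The last two are doubtful here. One primary objective asks what proportion of sinus infections follow a virus at all, and a child can contribute more than one episode. The figures show the direction and rough size of the gap and should not be printed as firm values.

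**What to change.** Reword two sentences in section 4, item i) Data Analysis, Aim 1.

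1. **Decision rule.** Conclude that rhinovirus is the leading antecedent only if its count among sinusitis episodes exceeds that of every other virus group, each comparison at a stated alpha and sidedness. Because every comparison must succeed, no multiplicity adjustment is needed; the rule is equivalent to testing rhinovirus against the observed runner-up. List the virus groups.
2. **Estimate.** Report the rhinovirus share minus the largest other share, with an interval that allows for repeat episodes within a child, for example by resampling children.
3. **Power sentence.** Limit it to a single rival at 20% with the others at about 15% or less, under independent episodes. Alternatively, give the lower figures for two or three rivals with their assumptions and the number of episodes used.

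The cost is the rewording alone; no new data, visits or assays are needed.

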1. Overview. This will be a prospective, longitudinal cohort study designed to include all symptomatic episodes of URI occurring in children between the ages of 49 and 84 months for a period of one year to determine relationships between bacterial colonization of the nasopharynx, acute viral URIs, and acute bacterial sinusitis. To accomplish this goal we will enroll approximately 355 children, ages 49 to 84 months, over a 40 month period (~9 children/month); with an expected attrition rate of 15% this will yield ~ 300 children. Nasal washes (for virus identification) and nasopharyngeal swabs (for nasopharyngeal bacterial culture and microbiota profiling) will be obtained at entry, and surveillance of both sites will be performed on four other occasions (February, April, September and December) throughout the one-year study. In addition, when acute upper respiratory symptoms develop, we will obtain nasal washes and nasopharyngeal swabs during the acute illness and again 1-2 weeks later during the period of spontaneous recovery or when the patient is diagnosed to have acute sinusitis. These samples will be obtained to identify infecting viruses and also to characterize the changes in bacterial microbiota associated with an acute URI and recovery versus an acute URI followed by a secondary bacterial sinus infection. The bacterial assemblages will be characterized using both standard bacteriologic techniques (which will allow semi-quantitation of recognized sinopathogens) and a high-density microarray (16S rRNA PhyloChip) in parallel with high-throughput 454-pyrosequencing (to validate array findings) to comprehensively describe the nasopharyngeal microbiome. Respiratory viruses will be identified from nasal washes using a molecular diagnostic system that can detect all common respiratory viruses (Respiratory MultiCode Assay, EraGen Biosciences).

Figure 2. Overview for Study Participant

Aim 1: To determine the incidence of acute bacterial sinusitis in children ≥ 4 through < 8 years of age (which is the peak age incidence of sinusitis) as a complication of an antecedent viral URI.

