b) Overcoming variability of the nasopharyngeal microbiome. Characteristics of nasopharyngeal colonization vary according to a variety of factors including attendance at day care, season, age, recent illness, socioeconomic status, etc¹⁰. To overcome this variability and still have a valuable baseline specimens that will permit comparison with an illness specimen, we will obtain surveillance specimens at entry and 4 other times. The specimens obtained closest in time preceding the episode of URI will be used as the baseline comparator.

c) Overcoming frequency of asymptomatic colonization with respiratory viruses. To interpret relationships between respiratory viruses and clinical illness, it is important to consider that respiratory viruses are detected in children without respiratory symptoms. The frequency of asymptomatic infection varies with age: viruses are detected in ~15% of healthy school-aged children and up to 31% of healthy infants.^{29,30} We will perform surveillance viral diagnostics on nasal wash samples at entry and 4 other occasions to estimate the seasonal frequency of asymptomatic infections for our study population; this information will be used as a reference point in analyses of viral infections during periods of illness.

d) Definition of Sinusitis: The 3 clinical presentations of sinusitis detailed in C.3.c above are widely accepted by 5 national societies: the American Academy of Allergy, Asthma and Immunology, the American Academy of Otolaryngic Allergy, the American Academy of Otolaryngology – Head and Neck Surgery, the American College of Allergy, Asthma, and Immunology, and the American Rhinologic Society.¹⁷ The American Academy of Pediatrics and the Infectious Diseases Society of America are including these presentations in their new guidelines (in press and PI is an author). In 4 clinical studies it has been shown that by using these stringent criteria, sinusitis is diagnosed in only 7-8% of respiratory infections presenting to the pediatrician.^{3,4,6,7}

e) Feasibility of enrollment, follow-up and Phylochip analysis. Both the principal investigator and the co-investigators have conducted several longitudinal studies over several years of large numbers of participants (daycare, asthma, birth cohort)^{2,29,30}. Subjects were recruited from the same practice that is participating in this study. The use of experienced coordinators and tested strategies for retention has led to excellent rates of

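### The surveillance-virus model names the wrong clustering; in the layouts examined that keep season, its dispersion factor leaves demographic tests anti-conservative if a child's specimens are positively correlated

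*Protocol*

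**What the plan says.** The second paragraph of the Aim 1 analysis (Protocol, section 4, item i) Data Analysis) concerns background virus in children without symptoms. Its data are introduced as "The specimens obtained at baseline and during four other surveillance periods (approximately 1500 - 1800 specimens"). The method is a robust multinomial regression, fitted with the R package multinomRob, which the protocol says "accounts for over-dispersion due to the clustering of the URI episodes within children". The purpose is to "assess the effect of season and the demographic variables on asymptomatic background viruses".

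Two other places fix the structure of these data. Existing Challenges, item c), states: "We will perform surveillance viral diagnostics on nasal wash samples at entry and 4 other occasions". The Overview says of the 355 children to be enrolled: "with an expected attrition rate of 15% this will yield ~ 300 children".

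The other two Aim 1 models deal with repeated observations on a child differently. The model for progression of a URI takes the child as the main sampling unit, and the model for sinusitis incidence has random effects. The surveillance model has no stated child-level term and relies on the dispersion factor alone. The protocol does not say whether a row of its data is one specimen, one child's total, or a cell defined by season and covariates.

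**The concern.** URI episodes do not enter this model, so the clustering that justifies the method is not the clustering present. The clustering present is among repeated specimens from the same child.

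The description is wrong, and the remedy it relies on may not work either. A dispersion factor compares the observed spread of counts with the spread that the multinomial predicts. It can detect within-child correlation only if a row holds several results from one child. The model is also meant to estimate a seasonal effect, and season changes between one child's specimens. Keeping season means splitting the child's specimens across rows, and the information about within-child correlation is then lost.

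What is at stake are the tests of factors that stay constant, or nearly so, within a child, such as siblings, day care and gender. If the standard errors treat a child's specimens as independent, these factors will be declared related to background virus more often than the nominal level allows.

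**Working it through.** **Inputs.** About 300 evaluable children from 355 enrolled (Overview); recruitment total of 360 (Table 2); five specimens per child, entry plus four (Existing Challenges c); background detection of about 15% (same item: "viruses are detected in ~15% of healthy school-aged children"). The protocol gives neither an intra-child correlation (ICC) nor a significance level for this test. ICCs from 0 to 0.3 and a two-sided 5% level are assumptions.

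**Step 1: reproduce the plan's figure.** 355 × 0.85 = 302, so about 300 children. 300 × 5 = 1500, 355 × 5 = 1775 and 360 × 5 = 1800. The stated range of 1500 to 1800 specimens is children times five surveillance specimens, which confirms the unit of data in this model.

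**Step 2: cost of ignoring the clustering.** For a child-level covariate and m = 5 specimens per child, the design effect is DE = 1 + (m − 1) × ICC = 1 + 4 × ICC. The true type I error of a nominal 5% test is 2 × [1 − Φ(1.96/√DE)], and the effective number of specimens is 1500/DE.

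Example at ICC 0.1: DE = 1.4, √DE = 1.183, 1.96/1.183 = 1.656, type I error 9.8%. The standard error is understated by 1 − 1/1.183 = 15%. At ICC 0.2 the understatement is 1 − 1/1.342 = 25%.

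| Assumed ICC | DE | True type I error | Effective specimens of 1500 |
|---|---|---|---|
| 0.01 | 1.04 | 5.5% | 1442 |
| 0.02 | 1.08 | 5.9% | 1389 |
| 0.05 | 1.20 | 7.4% | 1250 |
| 0.1 | 1.40 | 9.8% | 1071 |
| 0.2 | 1.80 | 14.4% | 833 |
| 0.3 | 2.20 | 18.6% | 682 |

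**Step 3: does a dispersion factor repair this?** A simulation used 300 children, five specimens each, 15% detection, a beta-binomial child effect, a binary child-level covariate with no true effect, and 1500 runs per ICC. The outcome was reduced to virus yes/no and the correction was a generic Pearson dispersion factor. Monte Carlo standard error at 5% is √(0.05 × 0.95/1500) = 0.006. Entries are mean dispersion estimate / type I error.

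| ICC | One row per specimen | One row per child | Season-by-covariate cells |
|---|---|---|---|
| 0 | 1.00 / 0.045 | 1.00 / 0.046 | 0.99 / 0.055 |
| 0.05 | 1.00 / 0.071 | 1.20 / 0.053 | 0.99 / 0.054 |
| 0.1 | 1.00 / 0.083 | 1.40 / 0.045 | 0.90 / 0.079 |
| 0.2 | 1.00 / 0.141 | 1.79 / 0.047 | 0.80 / 0.133 |
| 0.3 | 1.00 / 0.189 | 2.20 / 0.051 | 0.72 / 0.193 |

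*One row per specimen:* the variance of a single yes/no result is fixed by its mean, so the estimate stays at 1 whatever the correlation, and the inflation of step 2 remains.

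*Season-by-covariate cells:* the same children contribute to every season. Their shared effect moves the whole covariate group and is absorbed into the covariate estimate. The residual spread falls, roughly as 1 − ICC, when the correction needed is DE. The near-nominal 0.054 at ICC 0.05 owes something to the wide critical value (t with 10 cells − 6 parameters = 4 degrees of freedom).

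*One row per child:* the dispersion estimate tracks DE and the test holds its level. Each row now spans all seasons, so season cannot be a covariate.

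None of the three layouts gives valid tests of both stated effects.

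**The case against.** The strongest reply is that the protocol leaves the row unit open, that such detail normally belongs in an SAP (not available here), and that the sentence plainly intends to allow for clustering within children. Several stronger readings must be set aside on these grounds.

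- A reader might infer that a multinomial dispersion model cannot account for repeated samples from a child at all. It can: with child totals, type I error for a child-level factor was 0.045 to 0.053. What is lost there is season.
- A reader might infer that the named R package fails. The documents do not describe its variance estimators or input format, and the simulation did not run it. The argument rests only on the general property of single-result rows and season cells.
- A reader might take the inflation as established. It needs a positive ICC, which the documents do not give. Scheduled surveillance visits fall about two to five months apart (February, April, September, December), so a low correlation is plausible; at 0.01 to 0.02 the error is below 6%.
- A reader might infer that the protocol's reference level for interpreting viruses in illness is compromised. Existing Challenges c) defines that reference as a seasonal frequency. Season is largely a within-child contrast, and its test is not inflated in this way. The incidence and progression models are separate.
- A reader might infer that the multiplex assay rules out a multinomial outcome because one specimen can carry several viruses. The outcome categories are not defined, and a category for multiple detections would resolve this, so no contradiction is shown.

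What the reply does not answer is that the sentence names data not in this model, and that the paragraph requires season and demographics to be assessed by one method whose only stated protection does not work in the layouts examined that keep season. That goes beyond missing detail.

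**Conclusion.** The point holds in a limited form. The misnamed clustering is certain from the text. The statistical consequence is conditional: where season stays in the model, as specimen rows or season-by-covariate cells, tests of child-level demographic effects are anti-conservative if specimens from one child are positively correlated. By the design-effect formula, the true error of a nominal 5% test runs from about 5.5% to 14.4% for ICCs of 0.01 to 0.2. These rest on five specimens per child, a covariate constant within child, and assumed correlations.

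This is a supporting analysis of background virus within Aim 1, so the matter is minor, but it is cheap to put right before the data are analysed.

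**What to change.** In the Aim 1 analysis, replace the reference to URI episodes with surveillance specimens, and state that the unit of analysis is the specimen. Fit season as a within-child covariate alongside the demographic variables, with either a child random intercept or GEE with child as the cluster and robust standard errors. Either keeps season in the model and accounts for the within-child correlation explicitly; neither was simulated here.

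One practical form is a set of binary models, for any virus and for each main virus group, with a specimen positive for two viruses counted under each. This is a choice, not a necessity.

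The cost is a change of wording and standard software; a random-effects model is already planned for incidence. The downside of separate binary models is several models and more tests in place of one joint model of the virus mix, which matters a little because the same paragraph also wants to describe the diversity of viruses.
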